5 STUDY POPULATION

5.1 INCLUSION CRITERIA

Individuals must meet all of the following criteria to be eligible for study participation:

1. Aged ≥ 18 and ≤ 55 years.
2. Able to provide proof of identity to the satisfaction of the study clinician completing the enrollment process.
3. In good general health and without clinically significant medical history.
4. Able to provide informed consent.
5. Willing to have blood samples and data stored for future research.
6. Resides in or near Kalifabougou or Torodo, Mali, and available for the duration of the study.
7. Females of childbearing potential must be willing to use reliable contraception from 21 days prior to study day 0 through the final study visit as described below.
 - a. Reliable methods of birth control include 1 of the following: confirmed pharmacologic contraceptives via parenteral delivery or intrauterine or implantable device.
 - b. Nonchildbearing women will be required to report date of last menstrual period, history of surgical sterility (i.e., tubal ligation, hysterectomy) or premature ovarian insufficiency, and will have urine or serum pregnancy test performed per protocol.

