8.4.3 Withdrawal Criteria for an Individual Subject

An individual subject will be withdrawn from the study for any of the following:

- An individual subject's decision. (The investigator should attempt to determine the reason for the subject's decision.)
- Non-compliance with study procedures to the extent that it is potentially harmful to the subject or to the integrity of the study data.
- A change in the subject's condition as follows:
 - Loss of the ability to provide informed consent.
 - Withdraws permission to have blood samples or data stored for future research.
- The investigator determines that continued participation in the study would not be in the best interest of the subject.

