Any loss or unanticipated destruction of samples (for example, due to freezer malfunction) or data (for example, misplacing a printout of data with identifiers) that meets the definition of a reportable event will be reported to the FMPOS EC.

Additionally, subjects may decide at any point not to have their samples stored. In this case, the principal investigator will destroy all known remaining samples and report what was done to both the subject and to the EC. This decision will not affect the individual's participation in this protocol or any other protocols at NIH.

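### An enrolled subject who refuses sample storage must be withdrawn under section 8.4.3, but keeps participating under section 10.3

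*Combined protocol and SAP*

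**What the plan says.** Section 8.4.3 opens with a mandatory rule, "An individual subject will be withdrawn from the study for any of the following", and one of the criteria under it is "Withdraws permission to have blood samples or data stored for future research".

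Section 10.3 deals with the same act differently: "Additionally, subjects may decide at any point not to have their samples stored". In that case "the principal investigator will destroy all known remaining samples and report what was done to both the subject and to the EC", and "This decision will not affect the individual's participation in this protocol or any other protocols at NIH".

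Inclusion criterion 5 in section 5.1 makes storage an entry condition: "Willing to have blood samples and data stored for future research". It does not say what follows if a subject changes their mind after enrollment.

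**The concern.** An investigator faced with a subject who no longer wants blood samples stored cannot obey both sections. Applying 8.4.3 ends participation; applying 10.3 leaves it untouched. Two investigators, or the two clinics, could handle identical cases differently and each cite the protocol.

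What is at stake is follow-up of subjects who have already been dosed and would still attend. The primary efficacy endpoint is blood-smear infection through 24 weeks, analyzed as time to first infection (section 9.4.4). Under 8.4.3 such a subject is censored at withdrawal and the remaining scheduled safety visits lapse, for a reason unrelated to collecting either kind of data.

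**Working it through.** The conflict is textual, so the check sets the sections side by side.

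1. **Trigger.** Section 8.4.3 covers samples or data, kept for future research. Section 10.3 covers samples, without naming a purpose. A subject who refuses all sample storage also refuses it for future research, and so meets both triggers. A subject who refuses only data storage meets 8.4.3 alone, and nothing contradicts it.

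2. **Outcome.**

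| Event after enrollment | Section 8.4.3 | Section 10.3 |
|---|---|---|
| Refuses sample storage | Withdrawn from the study | Samples destroyed; participation unaffected |
| Refuses data storage only | Withdrawn from the study | Not addressed |

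3. **Ranking.** No section says which rule prevails. Criterion 5 governs entry. Section 10.4 records that consent to storage is taken at enrollment. Neither states the effect of a later change of mind.

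4. **Who is exposed.** Enrollment is the first artemether-lumefantrine dose, planned at day -14±7 (section 1.3.2). Efficacy-study subjects withdrawn before the infusion are replaced (section 8.4.3.2). Those withdrawn after it are not. The loss therefore falls on dosed subjects.

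5. **What stops and what remains.** Scheduled visits end. Section 7.2 encourages, but does not require, an early termination visit. Dosed subjects stay in the MITT set (section 9.3) and the safety dataset (8.4.3.2). Unresolved SAEs are followed to outcome as far as consent permits (8.4.2.3.2), and related SAEs that staff learn of later are still recorded (Table 2). The continued follow-up in 8.4.5.3 and 8.4.6.3 concerns pauses and halts, not these subjects.

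6. **What does not need storage for future research.** Smears are made from residual blood in the collection device, a finger prick or a small venipuncture (section 2.2.3.3). Adverse events are elicited by questioning and examination at each contact (section 8.4.2).

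7. **What may need stored material.** RT-PCR is run on coded dried blood spots at an outside university, and PK and ADA are run at NIAID (section 8.2.3), after the Bamako laboratory has processed and stored coded samples (section 2.2.3). The destruction order in 10.3 makes no exception for samples still awaiting these tests.

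8. **Does it bear on power?** The plan's own figure was reproduced first. Inputs from section 9.2.2: 110 per arm, 10% drop-out, placebo rate 0.4, protective efficacy 0.5 (so 0.2 on CIS43LS), two-sided alpha 0.025. Evaluable n = 0.9 × 110 = 99. For a pooled two-proportion z-test, power = Φ{[0.2 − 2.241 × √(2 × 0.3 × 0.7/n)] / √[(0.4 × 0.6 + 0.2 × 0.8)/n]}. At n = 99 this is Φ[(0.2 − 2.241 × 0.0651)/0.0636] = Φ(0.85) = 80.2%, against 80% in Table 4. At n = 98 it is 79.8%. The documents give no rate of storage refusal, so the extra loss at n = 98 is an assumption and not a finding.

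**The case against.** The best defense of 8.4.3 is criterion 5. If willingness to store is a condition of entry, removing subjects who withdraw it is coherent, and the documents would equally allow 10.3 to be corrected. This stands to the extent that the intended rule cannot be read from the text. It does not remove the conflict.

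Three stronger readings are tempting, and the documents support none of them.

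- *That the trial loses power.* Table 4 sits close to 80% in the row with placebo rate 0.4 and efficacy 0.5, so a reader might infer that any extra loss breaks the claim. Storage refusals are a form of drop-out and may fall within the planned 10%, at no cost. A fall from 80.2% to 79.8% still rounds to 80%. At placebo rates of 0.5 and 0.6 with the same efficacy, Table 4 gives 93% and 98%. The z-test also counts a withdrawn subject as wholly lost, whereas the primary time-to-event analysis uses the time up to censoring.
- *That withdrawal serves no analysis purpose and 10.3 is free of loss.* This holds for smears and adverse events. It does not hold for the secondary endpoints, because destruction under 10.3 could remove untested RT-PCR or PK material, and ADA samples as well.
- *That safety follow-up disappears, or that participants were misled.* Follow-up is cut short rather than absent. The consent pages are not available for review, so what participants were told cannot be judged.

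**Conclusion.** The point holds as an internal contradiction limited to blood samples: one event after enrollment has two opposite outcomes, and the plan cannot be followed as written. If 8.4.3 is applied, smear and scheduled safety follow-up of willing, dosed and unreplaced efficacy-study subjects ends early although the primary endpoint does not depend on storage for future research.

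The size is unknown because no refusal rate is given. That it is small is a judgment. No effect on power is claimed. The conclusion rests on reading a refusal of all sample storage as including storage for future research.

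**What to change.** Reconcile criterion 5 in section 5.1 with sections 8.4.3 and 10.3 so that refusal of sample storage has one stated consequence. The documents do not show which rule was intended. The option that keeps endpoint and safety data has three parts:

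- In 5.1, state that criterion 5 applies at entry.
- In 8.4.3, remove refusal of sample storage from the withdrawal list, so that scheduled smears, dried blood spots and safety visits continue. State separately what follows a refusal of data storage.
- In 10.3, limit destruction to samples held for future research, and have protocol-specified RT-PCR, PK and ADA testing completed first if the subject agrees.

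The consent text should be checked against the result.

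The cost is a small amendment, which needs EC approval before it takes effect (Statement of Compliance), and the loss of stored-sample research for the subjects concerned, which 10.3 already accepts.

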8.4.3.1 Re-enrollment and Unplanned Procedure Repetition

Unless otherwise specified within this protocol (e.g., rescreening as described in section 5.5), each person who is a subject in this study may be enrolled and may pass through each step and process outlined in the protocol, only **ONCE** (i.e., subjects may not "go back" and repeat a

Abbreviated Title: Anti-malaria MAb in Mali

Version Date: October 13, 2022

protocol step already completed). On a case-by-case basis, a request for re-enrollment, or for repetition of a protocol step or procedure already completed, may be submitted to, reviewed by, and approved by the SMM in writing. The SMM may also recommend or require consultation of the EC and/or DSMB and ISM.

8.4.3.2 Replacement of Withdrawn Subjects or Subjects Who Discontinue Study Agent

In the dose-escalation study, subjects withdrawn prior to the day 7 safety evaluation will be replaced. In the efficacy study, subjects withdrawn prior to study agent administration will be replaced.

All subjects exposed to study agents MUST be included in the safety dataset.

8.4.4 Additional Safety Oversight

8.4.4.1 Safety Review and Communications Plan

A safety review and communication plan (SRCP) is required for this protocol. The SRCP is an internal communications document between the principal investigators and the CSO, as sponsor representative, which delineates key safety oversight responsibilities of the principal investigators, the CSO, and other stakeholders. The SRCP includes a plan for conducting periodic safety surveillance assessments by the CSO.

8.4.4.2 Sponsor Medical Monitor

A SMM, representing the sponsor, has been appointed for oversight of safety in this clinical study. The SMM will be responsible for performing safety assessments as outlined in the SRCP.

8.4.4.3 Oversight Committees

8.4.4.3.1 Independent Safety Monitor in Mali

The ISM is an expert who does not have direct involvement in the conduct of the study and has no significant conflicts of interest as defined by NIAID policy. An ISM in Mali will review the study prior to initiation and will be available to advise the investigators on study-related medical issues and act as a representative for the welfare of the subjects. The ISM will conduct independent safety monitoring. The ISM is an expert in the field of oversight of clinical trials conducted in Mali and internal medicine, specifically in the population under study in Mali.

All deaths, SAEs, UPs, pregnancies, and FDA IND safety reports will be reported by the principal investigators to the ISM prior to or at the same time they are submitted to the EC or CSO unless otherwise specified herein. The ISM will be notified immediately if any pausing rule is met. The principal investigators will also notify the ISM if intentional or unintentional unblinding occurs. If the ISM is unblinded to the study agent given to an individual subject during medical management, the ISM will report that unblinding to the DSMB Executive Secretary. The ISM will have access to unblinded data, by group, only as the entire DSMB does. The ISM may also serve as an *ad hoc* member of the DSMB.

Abbreviated Title: Anti-malaria MAb in Mali

Version Date: October 13, 2022

8.4.4.3.2 Data and Safety Monitoring Board

The NIAID intramural DSMB includes independent experts that do not have direct involvement in the conduct of the study and have no significant conflicts of interest as defined by NIAID policy. The DSMB will review the study protocol, consent documents, and investigator brochure prior to initiation and twice a year thereafter, or as may be determined by the DSMB.

Additionally, the DSMB will conduct 1 interim analysis when safety data are available from the dose-escalation study subjects (section [9.4.8](#)).

The DSMB may convene additional reviews as necessary. The DSMB will review the study data as needed to evaluate the safety, efficacy, study progress, and conduct of the study.

All deaths, SAEs, UPs, pregnancies, and IND safety reports will be reported to the DSMB at the same time they are submitted to the EC and CSO unless otherwise specified herein.

All cases of intentional or unintentional unblinding will be reported to the DSMB not later than 1 business day from the time of study personnel awareness.

The principal investigators will notify the DSMB at the time pausing or halting criteria are met and obtain a recommendation concerning continuation, modification, or termination of the study.

8.4.5 Pausing Rules

“Pausing” is discontinuation of study intervention/treatment/dosing (agent/placebo/procedure, etc.) in a protocol-defined group or “arm,” until a decision is made to either resume or permanently discontinue such activity. Subjects continue to be followed for safety during a pause.

The pausing criteria for a group or arm (e.g., a specific dosing group) in this study include any one or more of the following:

- A subject experiences an SAE that is unexpected (per the investigator’s brochure or product label) and possibly, probably, or definitely related to a study agent;
- A subject experiences 2 grade 3 or greater AEs that are unexpected (per the investigator’s brochure or product label) and possibly, probably, or definitely related to a study agent.

The principal investigators or the CSO may also pause dosing/study interventions for one or more subjects for any safety issue. The study safety oversight bodies (e.g., DSMB, ISM) may recommend a pause to the CSO.

8.4.5.1 Reporting a Pause

If a pausing criterion is met, a description of the AE(s) or safety issue must be reported by the principal investigators within 1 business day to the CSO and the EC according to their requirements. The principal investigators will also notify the DSMB and ISM. In addition, the CSO or designee will notify all other site investigators by email or through the specified pathway.

Abbreviated Title: Anti-malaria MAb in Mali

Version Date: October 13, 2022

8.4.5.2 Resumption Following a Pause

The CSO, in collaboration with the principal investigators and DSMB and ISM, will determine if study activities, including agent administration and/or other study interventions may be resumed, and any additional modifications or requirements that may apply, for the impacted subject(s), or whether the events that triggered the pause require expansion to a study halt (see below).

The CSO or sponsor designee will notify the principal investigators of the decision. The principal investigators will notify the EC of the decision according to the EC's process.

8.4.5.3 Discontinuation of Study Agent

A subject who does not resume study agent/intervention/treatment will continue to be followed for protocol-specified safety assessments or as clinically indicated, whichever is more conservative.

8.4.6 Halting Rules for the Protocol

“Halting” is discontinuation of study intervention/treatment/dosing (agent/placebo/procedure, etc.) for all subjects in a study and suspension of enrollment until a decision is made to either resume or permanently discontinue such activity. Subjects continue to be followed for safety during a halt.

The halting rules are:

- Two or more subjects experience the same or similar grade 3 or greater AEs that are unexpected and possibly, probably, or definitely related to a study agent;

OR

- Any safety issue that the principal investigators or the CSO determines should halt the study. The study safety oversight bodies (e.g., DSMB) may recommend a halt to the CSO.

In addition, the FDA, Malian Ministry of Health, FMPOS EC, or any regulatory body having oversight authority may halt the study at any time. The DSMB or ISM may recommend a study halt.

8.4.6.1 Reporting a Study Halt

If a halting criterion is met, a description of the AE(s) or safety issue must be reported by the principal investigators, within 1 business day to the CSO and the EC according to their requirements. The principal investigators will also notify the DSMB and ISM. In addition, the CSO or designee will notify all other site investigators by email or through the specified pathway.

8.4.6.2 Resumption of a Halted Study

The CSO, in collaboration with the principal investigators and DSMB and ISM will determine if study activities, including enrollment, study agent administration, and/or other study interventions, may be resumed and any additional modifications or requirements that may apply.

Abbreviated Title: Anti-malaria MAb in Mali

Version Date: October 13, 2022

The CSO or sponsor designee will notify the principal investigators of the decision. The principal investigators will notify the EC of the decision according to the EC's process.

8.4.6.3 Discontinuation of Study Agent

Subjects who do not resume study agent/study intervention will continue to be followed for protocol-specified safety assessments or as clinically indicated, whichever is more conservative.

8.5 UNANTICIPATED PROBLEMS

8.5.1 Definition of an Unanticipated Problem

The definition of a UP is provided in section [8.4.1](#).

8.5.2 Unanticipated Problem Reporting

The investigator will report UPs to the FMPOS EC according to NIH Human Research Protection Program (HRPP) Policy 801, as described in section [8.6.1](#).

8.6 ADDITIONAL REPORTING REQUIREMENTS

8.6.1 Reporting to the FMPOS EC

Non-compliance and other reportable events will be reported to the FMPOS EC according to NIH HRPP Policy 801, which requires reporting as described below.

The following will be reported within 7 calendar days of any investigator or individual associated with the protocol first becoming aware:

- Actual or suspected noncompliance.
- Actual or suspected major deviation.
- Actual or suspected UPs.
- New information that might affect the willingness of a subject to enroll or remain in the study.
- Suspension or termination of research activities, including holds on new enrollment, placed upon the research by the sponsor, NIH or NIAID leadership, or any regulatory agency.

Any death of a research subject that is possibly, probably, or definitely related to the research must be reported within 24 hours of the investigator becoming aware of the death.

Additionally, investigators must provide the following information to the EC in summary format at the time of continuing review, or when otherwise specifically requested by the EC or the Office of Human Subjects Research Protections (OHSRP) Office of Compliance and Training:

- Major and minor protocol deviations.
- Noncompliance reported to the EC that is not related to a protocol deviation.
- AEs and SAEs that do not meet the definition of an UP.
- UPs reported to the EC.

Abbreviated Title: Anti-malaria MAb in Mali

Version Date: October 13, 2022

8.6.2 Reporting to the NIAID Clinical Director

The principal investigator will report UPs, major protocol deviations, and deaths to the NIAID clinical director according to institutional timelines.

8.6.3 Reporting Protocol Deviations that Result from the COVID-19 Pandemic

The following addresses the reporting requirements to the FMPOS EC with regard to protocol deviations that result from disruption of study visits from the COVID-19 pandemic. These requirements follow the direction of the FMPOS EC as well as the NIH reporting requirements.

Investigators may modify the protocol without prospective FMPOS EC approval when necessary to prevent an immediate apparent harm to a study subject. Typically, when this occurs the event must be reported to the EC via a Reportable Event Form (REF) within 7 days of the deviation. Given the potential need for this to occur on a much larger than usual scale, it is not required that all planned deviations be reported to the FMPOS EC in an expedited timeframe. Only those deviations which meet the definition of a major deviation will require reporting, as defined in section 8.4.1.

If a subject cannot complete a protocol-specified study visit or intervention, the principal investigator should assess the impact of the missed visit on the safety of the subject and the scientific validity of the trial. If in the principal investigator's determination neither of these are meaningfully impacted by the deviation, these do not need to be reported to the FMPOS EC in an expedited manner. The event should be included in the summary of events reported at the time of continuing review.

If in the opinion of the principal investigator the missed visit or intervention poses a risk to the safety of the subject, the investigator should develop a plan to minimize the impact of the deviation. For example, if the subject is scheduled to return to the study site for safety lab work, the investigator may arrange for labs to be drawn at a location closer to the subject's home. In cases such as this, if the change is necessary to assure the safety of the subject, the investigator may implement the change without prospective FMPOS EC approval. If the change meets the definition of a major deviation, it must be reported via a REF within 7 days.

9 STATISTICAL CONSIDERATIONS

9.1 STATISTICAL HYPOTHESIS

The hypotheses are that CIS43LS will be safe and will confer protection against Pf infection. In the dose-escalation study, the primary objective is to evaluate the safety and tolerability. In the efficacy study, the primary objective is to evaluate the safety and efficacy of CIS43LS compared to placebo.

Primary Endpoints:

- Dose escalation: Incidence and severity of local and systemic AEs occurring within 7 days after the administration of CIS43LS
- Efficacy: Pf blood stage infection as detected by microscopic examination of thick blood smear for 24 weeks after administration of CIS43LS or placebo

Abbreviated Title: Anti-malaria MAb in Mali

Version Date: October 13, 2022

Secondary Endpoints:

- Dose escalation: Measurement of CIS43LS in sera of recipients
- Efficacy: Pf blood stage infection as detected by RT-PCR for 24 weeks after administration of CIS43LS or placebo
- Efficacy: Measurement of CIS43LS in sera of recipients

